8.2 Method of Treatment Assignment, Randomization

Patients who meet all eligibility criteria may be considered for randomization. Eligibility of all patients will be reviewed and approved for randomization by the Sponsor's Medical Monitor, or designee. Patients approved for randomization will be randomized 2:1 to receive one instillation of 8 mg Qapzola or one instillation of placebo.

The randomization plan will use a permuted block design and will not be stratified. Study drug kits will contain either vials of Qapzola, or placebo and will be patient specific. Patients will be randomized within a center. Patient numbers will be assigned sequentially at each site.

8.3 Analysis Populations

Four datasets will be analyzed:

- **Target (Low- to Intermediate-Risk) Population:** all randomized patients with confirmed low- or intermediate-risk NMIBC as per the AUA Guidelines. The analysis population for all efficacy endpoints will be the Target (low- or intermediate-risk NMIBC) Population based on local pathology.
- **Non-Target Population:** all randomized patients other than the Target Population defined above. No primary efficacy endpoint analysis will be provided in this population as they will not be under follow-up. Only safety analysis will be performed using this population.
- **Per-Protocol Population:** patients in the Target Population excluding patients with major protocol deviations and who received additional medications for NMIBC during the follow-up and prior to recurrence.
- **Safety Population:** all randomized patients classified according to the actual treatment received, regardless of random assignment.

8.4 General Statistical Methods

Spectrum's Biostatistics and Data Management (BDM) group will be responsible for data management and statistical analysis of this study. All statistical analyses will be performed using SAS for Windows (version 9.3 or higher). Patient data listings and tabular presentations of results by treatment arms will be provided. Further details of the criteria and conduct of the statistical analyses will be included in the Statistical Analysis Plan for this study.

8.5 Efficacy Analyses

8.5.1 Efficacy Assessments

The primary efficacy assessment will be time to recurrence with any pathologically confirmed disease of \geq Ta histology or CIS post-treatment. These patients will be assessed cystoscopically and by urine cytology at 3 months (\pm 30 days) intervals calculated from the date of TURBT for the first 2 years and then every 6 months (\pm 60 days) for the remainder of the follow-up or until recurrence, whichever occurs first. The date of the cystoscopy or TURBT procedure when the bladder tumor was detected and which was confirmed histologically by pathology review will be used as the date of recurrence. Only the first documented recurrence will be used to assess the primary efficacy.

The disease recurrence will be determined exclusively using the pathology review of biopsied tumors when detected by the cystoscopy. The current study excludes patients with disease of upper tract or prostatic urethra. If the urine cytology is positive but the pathology review of the biopsy is negative, this may lead to the examination of upper tract disease. A urine cytology may be performed to rule out the upper tract urothelial carcinoma at any follow-up time point.

8.5.2 Primary Endpoint

- **Time to Recurrence** in patients with low- to intermediate-risk non-muscle invasive bladder cancer (NMIBC) who receive either 8 mg Qapzola or placebo post transurethral resection of bladder tumor (TURBT)

8.5.3 Secondary Endpoints

1. 2-Year Recurrence Rate
2. Extent of Disease at Recurrence (number and location of tumors)
3. Time to Disease Progression (based on the tumor stage)

8.5.4 Definitions

- **Recurrence:** any pathologically confirmed disease of \geq Ta histology or CIS post-treatment
- **Progression:** any pathologically confirmed disease of \geq T2

8.5.5 Primary Endpoint - Time to Recurrence

The Time to Recurrence is defined as time from Day 1 treatment to the date of the first histologically confirmed recurrence as described in [Section 8.5.1](#) above. Patients without a recurrence at the time of the primary analysis will be censored at the last available date of cystoscopy. Patients who died due to any cause before confirmed recurrence will be censored at the last available date of cystoscopy.

The primary analysis will be conducted using a hierarchical procedure of hypothesis testing at a 5% level of significance. The primary endpoint, Time to Recurrence, will be examined first, and if significant, the secondary endpoint, 2-Year Recurrence Rate, will be examined next, and if also significant, Extent of Disease at Recurrence, and Time to Disease Progression will then be examined.

The primary endpoint of Time to Recurrence will be analyzed using the Target Population as defined in [Section 8.3](#). The primary analysis of Time to Recurrence will be conducted once a total of 208 recurrence events are accrued in the study. The primary endpoint analysis involves a 2-sided log-rank test of time to recurrence between two treatment groups at 5% level of significance. Distribution of Time to Recurrence will be estimated using the Kaplan-Meier product-limit method. The median times to recurrence with two-sided 95% confidence intervals (CI) will be estimated, together with the estimates at 6, 12, 18 and 24 months. The hazard ratio and corresponding 95% CI of the treatment effect will be estimated from a Cox proportional hazard regression model with treatment arm as the only covariate and tested using a likelihood ratio test at the level of significance described above. Additional exploratory analysis of Cox proportional hazard regression will be used to estimate the hazard ratio and its 95% CI. The model will include treatment effect, study center, low vs intermediate risk, primary vs. recurrent disease as stratification factor in addition to any other baseline or demographics factors.

In addition, the following additional sensitivity analyses of Time to Recurrence will be provided:

- a. Excluding patients who miss 2 consecutive cystoscopies or lost to follow-up either prior to recurrence or prior to the date of the primary analysis – Completer analysis
- b. Excluding patients who miss 2 consecutive cystoscopies or lost to follow-up either prior to recurrence or prior to patient's follow-up duration of 24 months – Completer 24 Month analysis
- c. Treating patients with no recurrence who miss 2 consecutive cystoscopies or lost to follow-up prior to date of the primary analysis as recurred.

The following patients will be considered as protocol deviations and will be excluded from the analysis of Time to Recurrence using the Per-Protocol Population as exploratory:

- Patients with Day 1 instillation that do not occur between 30 and 90 minutes post-TURBT
- Patients whose follow-up cystoscopy occurs outside the ± 30 -day window
- Patients who received other treatment for NMIBC prior to recurrence will be censored at the last assessment prior to the treatment

8.5.6 Secondary Endpoints

8.5.6.1 2-Year Recurrence Rate

The **2-Year Recurrence Rate** is the proportion of patients who have a confirmed recurrence before or at the 2-year follow-up visit (Visit 10) for each study arm. The treatment effect will be analyzed only if a significant treatment effect ($p < 0.05$) is identified for the primary endpoint, **Time to Recurrence**. The analysis will calculate odds ratio with 95% CI and apply Cochran-Mantel-Haenszel chi-square test. The recurrence rate will also be estimated using the Kaplan-Meier product-limit method along with 95% CI. Since visits do not often occur at the specified intervals, a cut-off upper limit of 765 days from Day 1 treatment will be used for the 24 month visits.

8.5.6.2 Extent of Disease at Recurrence

Extent of disease at recurrence, including changes in number and in locations of tumors from Day 1 to recurrence, will be examined for patients with recurrence only by each treatment arm. The change in number will be summarized using quantiles. The location of all tumors will be recorded at Day 1 and at recurrence for each patient. Locations include base, dome, neck, trigone, anterior wall, posterior wall, left wall, and right wall. For each location, the number of patients (and percentage) who had tumor at that location will be summarized by at Day 1 only, at recurrence only, at both Day 1 and recurrence, and at neither. The discordance rate of each location will also be calculated.

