The Time to Recurrence is defined as time from Day 1 Treatment to the date of the first histologically confirmed recurrence (using the date of corresponding cystoscopy) of the patient's bladder tumor. Patients without recurrence at the time of the primary analysis will be censored at the last available date of cystoscopy. Patients who died due to any cause before confirmed recurrence will be censored at the last available date of cystoscopy.

The following sensitivity analyses will be performed for the primary analysis.

1. Analysis of time to recurrence by excluding patients who miss 2 consecutive cystoscopies or lost to follow-up either prior to recurrence or prior to the date of the primary analysis – Completer analysis
2. Analysis of time to recurrence by excluding patients who miss 2 consecutive cystoscopies or lost to follow-up either prior to recurrence or prior to patient's follow-up duration of 24 months – Completer 24 Month analysis
3. Analysis of time to recurrence by considering patients with no recurrence who miss 2 consecutive cystoscopies or lost to follow-up prior to date of the primary analysis as recurred.

The primary analysis will be conducted using a hierarchical procedure of hypothesis testing at a 5% level of significance. The primary endpoint, Time to Recurrence, will be examined first, and if significant, the secondary endpoint, 2-Year Recurrence Rate, will be examined next, and if also significant, Extent of Disease at Recurrence, and Time to Disease Progression will then be examined in that order.

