1.4 Study Rationale

All expert urology societies recommend a high quality TURBT as the initial treatment for patients with NMIBC. However, despite the improvements in instrumentation and surgical techniques, there continues to be a high frequency of tumor recurrence and progression of the disease to more advanced stages. Therefore, a key focus for improving the treatment of NMIBC is to identify new treatment strategies that reduce the rate of recurrence and progression.

The medical literature supports, and international guidelines recommend, immediate instillation of a chemotherapeutic agent following TURBT because of its potential impact in reducing tumor recurrence. Theoretically, the high rate of tumor recurrence is attributed to a number of putative factors:

- Incomplete initial tumor resection
- Inability to visualize all tumors
- Implantation of floating tumor cells, which are released into the bladder during TURBT
- Growth of a new tumor due to unknown or poorly understood factors predisposing to the development of bladder cancer.

The goal of immediate postoperative instillation of a chemotherapeutic agent into the bladder is to decrease recurrence rates by destroying floating tumor cells released during the TURBT procedure, which have the potential to implant in the bladder wall. Postoperative instillation of a chemotherapeutic agent may also provide benefit by ablating residual tumor cells remaining at the resection site.

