8.1 Sample Size

The enrolled patients will be randomized in a 2:1 ratio to either Qapzola or placebo. The primary endpoint is Time to Recurrence in the Target Population. The primary endpoint analysis involves a test of comparison: 8 mg Qapzola vs. placebo using 2-sided log-rank test at 5% level of significance.

The sample size calculation assumes a hazard ratio (HR) of 0.65 based on the results from previous Phase 3 studies of Qapzola and placebo comparisons overall and in the drug instillation time window 31-90 minutes post-TURBT as described in [Section 1.3.1.2](#) and [Section 1.3.1.4](#) respectively.

Approximately 500 patients will be enrolled and treated in this study. Accrual time is estimated as 24 months and follow-up time as 24 months. For the sample size calculation, the HR of 0.65 is assumed for the improvement in time to recurrence in favor of Qapzola as compared to the Placebo with a hazard rate of 0.3. In a 2:1 randomization of Qapzola and Placebo, sample sizes of 425 Target disease patients (284 in Qapzola and 141 in Placebo) will provide 85% power. This sample size is estimated to provide a total of 208 recurrence events during the follow-up duration of at least 24 months. The sample size calculation was based on PASS 14 (NCSS, LLC, Kaysville, Utah).

Since the Target population is confirmed by pathology review and this will be performed after patients are randomized and have undergone TURBT procedure, the study will account for misclassification in the Target disease population. Accounting for 15% misclassification of randomized patients, the study will enroll approximately 500 patients. However, the study will continue to enroll patients until the required number of Target disease patients are accrued.

A futility analysis will be performed during the study conduct to determine the study continuation. The futility analysis will be conducted in the Target patients once 60 events are observed. The study will be stopped for futility if the calculated z-value from the log-rank test of HR is >1.0 . No adjustment for multiplicity of comparison will be made for futility analysis and the final analysis will be performed at 5% level of significance.

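### Extent of Disease at Recurrence sits in the 5% testing hierarchy but compares the arms in recurrers only, a subset that treatment itself selects, so the comparison is not randomized and can be biased in either direction

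*Protocol*

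**What the plan says.** Protocol 8.5.6.2 defines the endpoint as changes in the number and location of tumors between Day 1 and recurrence, and says these "will be examined for patients with recurrence only by each treatment arm". On number it adds: "The change in number will be summarized using quantiles". Location is tabulated as counts, percentages and discordance rates. The section names no test, effect measure or confidence interval.

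Section 8.5.5 nevertheless places the endpoint inside a hierarchical hypothesis-testing procedure at the 5% level. Once Time to Recurrence and the 2-Year Recurrence Rate are significant, "if also significant, Extent of Disease at Recurrence, and Time to Disease Progression will then be examined". The synopsis fixes the sequence: "Extent of Disease at Recurrence, and Time to Disease Progression will then be examined in that order".

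Section 2.2 states the objective for patients who receive Qapzola or placebo, not for those who recur. Section 8.3 makes the Target Population the analysis set for all efficacy endpoints.

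SAP 1.0 (Summary of Changes; Sections 3.4.1, 4.7 and 6) removes every efficacy objective, endpoint and analysis after early termination.

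**The concern.** Recurrence occurs after randomization and is the primary endpoint. Restricting the comparison to recurrers conditions on an outcome that treatment affects, and the hierarchy ensures that the test is reached only when that effect has been declared. The two recurrer groups then need not be alike, even if the drug changes no tumor that does come back. A prevented recurrence, the best possible result for extent of disease, contributes nothing.

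The protocol gives a reason to expect different mixes. Section 1.4 lists several putative sources of recurrence, including implantation and new tumor growth. It gives the goal of instillation as "destroying floating tumor cells released during the TURBT procedure, which have the potential to implant in the bladder wall". If one source is suppressed more than another, and the sources differ in tumor number, the mix among recurrers shifts by arm. A working drug could then appear to give more extensive recurrences, or a selection artefact could be claimed as a further benefit.

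**Working it through.** **1. Inputs from the protocol (8.1 and synopsis).** 284 Qapzola and 141 placebo Target patients; HR 0.65; placebo hazard 0.3 (read as per year, since no unit is stated); 24 months' accrual plus 24 months' follow-up; 208 events.

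**2. Reproducing the event count.** With exponential times, uniform accrual over 2 years, 4 years in total and no dropout, P(event) = 1 − [exp(−2λ) − exp(−4λ)]/(2λ).
- Placebo, λ = 0.30: 0.587, so 141 × 0.587 ≈ 83.
- Qapzola, λ = 0.195: 0.439, so 284 × 0.439 ≈ 125.
- Total ≈ 208, as stated.

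About 59% of placebo and 44% of Qapzola patients would enter the comparison.

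**3. Assumptions not in the documents.** The placebo hazard is split equally, 0.15 implantation and 0.15 new tumor. The drug acts on implantation only, 0.045 against 0.15, which keeps the overall HR at (0.045 + 0.15)/0.30 = 0.65. 20% of implantation recurrences and 50% of new-tumor recurrences are multifocal, in both arms. The drug has no effect on the number of tumors in any recurrence.

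**4. Mix among recurrers.** The implantation share is 0.15/0.30 = 50% on placebo and 0.045/0.195 = 23.1% on Qapzola.

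| Multifocal share, implantation/new | Placebo recurrers | Qapzola recurrers |
|---|---|---|
| 20%/50% | 0.5×0.2 + 0.5×0.5 = 35% | 0.231×0.2 + 0.769×0.5 = 43% |
| 50%/20% | 35% | 0.231×0.5 + 0.769×0.2 = 27% |
| 30%/40% | 35% | 0.231×0.3 + 0.769×0.4 = 38% |
| equal (35%) | 35% | 35% |

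**5. Same model, all Target patients, 24 months.** At 20%/50%, multifocal first recurrence is (1 − e^(−0.60)) × 0.35 = 0.451 × 0.35 = 15.8% on placebo and (1 − e^(−0.39)) × 0.431 = 0.323 × 0.431 = 13.9% on Qapzola. Recurrers look worse on Qapzola, while randomized patients do better.

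**6. False significance by simulation.** Two-sided 5% Mann-Whitney test among recurrers, 3,000 to 4,000 trials per scenario; nominal rate 2.5% in each direction. Number is 1 if solitary and 2 + Poisson(1) if multifocal. For change from Day 1, 60% have a single lesion at baseline (the approximate figure for the earlier Phase 3 studies in 1.3.1), assumed independent of recurrence type.

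| Shares | Raw number at recurrence | Change from Day 1 (the protocol's measure) |
|---|---|---|
| 20%/50% | about 20%, against Qapzola | about 11%, against Qapzola |
| 50%/20% | 22–25%, for Qapzola | about 11%, for Qapzola |
| 30%/40% | 5–6%, against Qapzola | about 4%, against Qapzola |
| equal | no bias | no bias |

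**7. A second model.** Here patients differ by single or multifocal disease at Day 1 (60/40, equal placebo hazards), and the drug's HR is 0.5 in single and 0.8 in multifocal disease. With mean tumors at recurrence of 1.3 and 3.0, raw number is falsely worse on Qapzola in 12% of trials. The mean change from Day 1 is then the same in both strata, and the test on change shows no bias (about 2% each way). With a multifocal mean of 2.0, the mean change differs between strata, and the test on change is falsely better in 8%. With a uniform HR of 0.65 there is no shift. So subtracting baseline can shrink or reverse the bias, but it does not remove the selection.

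**The case against.** **SAP 1.0 drops the endpoint.** This stands in full. A reader might infer that a reported Qapzola result is distorted. The documents do not support that, because no efficacy result is to be produced.

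**8.5.6.2 is already descriptive.** Its text is, and it names no test. But the synopsis and 8.5.5 list the endpoint as a step in hypothesis testing at 5%, and nothing labels it descriptive. The conflict has to be settled one way.

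**The mechanism is inferred.** A reader might take Section 1.4 to say that the drug prevents implantation and leaves new tumors untouched, so that Qapzola recurrers are enriched for new tumors. It does not say so. The sources are offered as theoretical, and the section adds that residual cells at the resection site may be ablated. Selective prevention is plausible, not stated.

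**The size depends on invented inputs.** This also stands. The hazard split, the implantation-only effect and the multifocal shares are all assumptions. The rates are also unconditional. On raw number, requiring a significant 2-year rate as well lowers 20% to about 15% of trials.

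**The replacement largely re-measures recurrence.** This is correct and is carried into the cost below.

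**Conclusion.** The point holds for the protocol design only. A step of the confirmatory hierarchy compares arms within a subset defined by a treatment-affected outcome, and no other section repairs this. The comparison is not randomized, and the bias can go either way.

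On the protocol's own measure, the false-significance rate in one direction is about 11% against 2.5% under the implantation-only model with 20%/50% shares or the reverse. It is about 4% with 30%/40% shares, and there is no bias with equal shares. The figure of about 20% belongs to raw tumor number, which is not the planned measure, and should not be quoted as the size of the problem. Nor do the documents support a claim that the bias would run against Qapzola, or that it must occur.

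**What to change.** In 8.5.6.2, state that the recurrers-only tables of number and location are descriptive, with no between-arm inference. In the hierarchy (8.5.5 and synopsis), replace them with the cumulative incidence of multifocal first recurrence by Month 24 in all Target patients. Solitary first recurrence is a competing event, and recurrence-free patients not yet at 24 months are censored. Name the test and the interval estimate. The 765-day limit in 8.5.6.1 can define Month 24.

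The cost is wording and one extra table. Tumor number is already to be recorded at cystoscopy and TURBT (5.4.8, 5.4.9).

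The downside should be written into the plan. The measure combines prevention with extent, overlaps substantially with Time to Recurrence and the 2-Year Recurrence Rate, and cannot show an effect on extent separate from prevention. With equal shares, where the drug leaves the multifocal share of recurrences unchanged, it still differs by arm: 0.451 × 0.35 = 15.8% against 0.323 × 0.35 = 11.3%, significant in about 26% of trials. With 50%/20% shares it is significant in about 59%, and with 20%/50% in about 8%. Location stays descriptive.

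Because SAP 1.0 has removed efficacy, the change matters only if this protocol's plan is used again.

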8.5.6.3 Time to Disease Progression

Time to Progression is the time from Day 1 to the first documentation of stage progression as confirmed by pathology. Only the development of $\geq T2$ disease will be included in the assessment of time to disease progression. Censoring of patients with no documented progression will be the same as described for recurrence in [Section 8.5.5](#) above.

Distribution of Time to Progression will be estimated using the Kaplan-Meier method. Analysis of Time to Progression will be similar to the analysis of Time to Recurrence, above.

8.6 Safety Evaluation

Patients will be evaluated for safety if they have received any study treatment (Safety Population), and classified according to the treatment received.

8.6.1 Safety Endpoints

- All AEs

- Related Adverse Events
- Serious Adverse Events (SAEs)
- AEs leading to drug discontinuation
- Vital signs (body temperature, blood pressure, and heart rate) and routine laboratory parameters (hematology, chemistry)
- Deaths

8.6.1.1 Adverse Events

All treatment emergent adverse events will be graded according to National Cancer Institute Common Terminology Criteria for Adverse Events (NCI CTCAE) version 4.03, and grouped by the MedDRA Preferred Term, and summarized by worst grade severity per patient.

